4 OBJECTIVES AND ENDPOINTS

Table 4-1: Objectives and Endpoints

Objectives	Endpoints
Primary	

 To compare the PFS of BMS-986207 in combination with nivolumab plus ipilimumab (Arm A) versus nivolumab plus ipilimumab (Arm B) in participants with 1L Stage IV NSCLC expressing PD-L1 \geq 1% 	
 PFS in participants with tumors expressing PD-L1 \geq 1% based on RECIST v1.1 by BICR
Secondary	

 To compare the PFS of BMS-986207 in combination with nivolumab plus ipilimumab (Arm A) versus nivolumab plus ipilimumab (Arm B) in all randomized participants with 1L Stage IV NSCLC 	
 PFS in all randomized participants based on RECIST v1.1 by BICR

 To assess the safety and tolerability of BMS-986207 in combination with nivolumab plus ipilimumab (Arm A) and nivolumab plus ipilimumab (Arm B) in participants with 1L Stage IV NSCLC 	
 Incidence of AEs, SAEs, AEs leading to discontinuation, and deaths

 To estimate the ORR of BMS-986207 in combination with nivolumab plus ipilimumab (Arm A) and nivolumab plus ipilimumab (Arm B) in all randomized participants with 1L Stage IV NSCLC and in subgroups defined by PD-L1 expression 	
 ORR in all randomized participants and in subgroups defined by PD-L1 expression (PD-L1 \geq 1% , < 1%, 1% - 49%, and \geq 50%) based on RECIST v1.1 by BICR assessment

Table 4-1: Objectives and Endpoints

Objectives	Endpoints

 To compare OS of BMS-986207 in combination with nivolumab plus ipilimumab (Arm A) versus nivolumab plus ipilimumab (Arm B) in randomized participants with tumors expressing PD-L1 $\geq 1\%$ 	
 OS in participants with tumors expressing PD-L1 $\geq 1\%$

 To compare OS of BMS-986207 in combination with nivolumab plus ipilimumab (Arm A) versus nivolumab plus ipilimumab (Arm B) in all randomized participants with 1L Stage IV NSCLC 	
 OS in all randomized participants

 To compare the PFS of BMS-986207 in combination with nivolumab plus ipilimumab (Arm A) versus nivolumab plus ipilimumab (Arm B) in all randomized participants and in participants with tumors expressing PD-L1 $\geq 1\%$ with 1L Stage IV NSCLC 	
 PFS in all randomized participants and in participants with tumors expressing PD-L1 $\geq 1\%$ based on RECIST v1.1 by investigator's assessment

 To estimate the PFS of BMS-986207 in combination with nivolumab plus ipilimumab (Arm A) and nivolumab plus ipilimumab (Arm B) in participants with 1L Stage IV NSCLC in subgroups defined by PD-L1 expression 	
 PFS in subgroups defined by PD-L1 expression (PD-L1 $< 1\%$, $1\% - 49\%$, and $\geq 50\%$) based on RECIST v1.1 by BICR and investigator's assessment

 To estimate the ORR of BMS-986207 in combination with nivolumab plus ipilimumab (Arm A) and nivolumab plus ipilimumab (Arm B) in all randomized participants with 1L Stage IV NSCLC and in subgroups defined by PD-L1 expression 	
 ORR in all randomized participants and in subgroups defined by PD-L1 expression (PD-L1 $\geq 1\%$, $< 1\%$, $1\% - 49\%$, and $\geq 50\%$) based on RECIST v1.1 by investigator's assessment

 To estimate the DOR of BMS-986207 in combination with nivolumab plus ipilimumab (Arm A) and nivolumab plus ipilimumab (Arm B) in all randomized participants with 1L Stage IV NSCLC and in subgroups defined by PD-L1 expression 	
 DOR in all randomized participants and in subgroups defined by PD-L1 expression (PD-L1 $< 1\%$, $\geq 1\%$, $1\% - 49\%$, and $\geq 50\%$) based on RECIST v1.1 by BICR and investigator's assessment

 To estimate OS of BMS-986207 in combination with nivolumab plus ipilimumab (Arm A) and nivolumab plus ipilimumab (Arm B) in subgroups defined by PD-L1 expression 	
 OS in subgroups defined by PD-L1 expression ($< 1\%$, $1\% - 49\%$ and $\geq 50\%$)
Exploratory	

 To characterize the PK and immunogenicity of BMS-986207, nivolumab, and ipilimumab when administered in combination 	
 Summary measures of C_{trough} and EOI concentrations, incidence of ADA to BMS-986207, nivolumab, and ipilimumab, summary measures of ADA titers and kinetics (onset and duration), and assessments of ADA effect on efficacy, safety, and PK

 To explore the pharmacodynamic activity of BMS-986207 administered in combination with nivolumab and ipilimumab via assessment of translational biomarkers 	
 Summary measures of change (or % change) from baseline in intratumoral and peripheral biomarkers of immune activation and their association with anti-tumor activity

Table 4-1: Objectives and Endpoints

Objectives	Endpoints

 To explore potential associations between anti-tumor activity and select biomarker measures in the tumor and peripheral blood prior to treatment 	
 Summary measures of anti-tumor activity by pretreatment level of biomarkers of interest

 To characterize the threshold for meaningful change in disease-related symptoms as measured by the NSCLC-SAQ in participants with Stage IV NSCLC 	
 Analysis of meaningful change threshold for the NSCLC-SAQ total score based on the PGIS and PGIC as anchor measures

 To characterize changes in disease related symptoms and health-related quality of life in participants with Stage IV NSCLC 	
 Mean change from baseline in NSCLC-SAQ total score and FACT-G7

 To characterize patient-reported health status in participants with Stage IV NSCLC 	
 Mean change from baseline in EQ-5D-5L utility index and EQ VAS scores

Abbreviations: 1L, first-line; ADA, anti-drug antibody; AE, adverse event; BICR, blinded independent central review; Ctrough, observed serum trough concentration; DOR, duration of response; EOI, end of infusion; EQ-5D-5L, 5 Level EQ-5D Questionnaire; EQ VAS, EuroQol visual analog scale; FACT-G7, Functional Assessment of Cancer Therapy - General - 7 item version; NSCLC, non-small cell lung cancer; NSCLC-SAQ, Non Small Cell Lung Cancer Symptom Assessment Questionnaire; ORR, objective response rate; OS, overall survival; PD-L1, programmed death-ligand 1; PFS, progression-free survival; PGIC, Patient Global Impression of Change; PGIS, Patient Global Impression of Severity; PK, pharmacokinetic; RECIST, Response Evaluation Criteria in Solid Tumors; SAE, severe adverse event.

5 STUDY DESIGN

[figure not shown]
5.1 Overall Design

This multi-center, randomized Phase 2 trial will evaluate the efficacy and safety of BMS-986207 in combination with nivolumab plus ipilimumab versus nivolumab plus ipilimumab in adult participants with 1L Stage IV NSCLC. All participants will complete up to 3 study periods: screening (up to 28 days), treatment (up to 2 calendar years regardless of treatment delays [up to 18 cycles, 42 days/cycle]), safety follow-up (100 days from last dose of study intervention), response follow-up (up to 2 years from last dose of study intervention), and survival follow-up (up to 4 years from randomization). The duration of study participation will be approximately 4 years.

Images will be submitted to a central imaging vendor and may undergo Blinded Independent Central Review (BICR) at any time during the study. Prior to scanning the first participant, sites should be qualified and understand the image acquisition guidelines and submission process as outlined in the CA020016 Imaging Manual provided by the central imaging vendor.

The study design schematic is presented in [Figure 5.1-1](#).

Figure 5.1-1: Study Design Schema

Abbreviations: 1L, first-line; ALK, anaplastic lymphoma kinase; ECOG, Eastern Cooperative Oncology Group; EGFR, epidermal growth factor receptor; IHC, immunohistochemistry; N, number; NSCLC, non-small cell lung cancer; PD-L1, programmed death-ligand 1; ROS-1, c-ros oncogene 1; Q3W, every 3 weeks; Q6W, every 6 weeks.

5.1.1 Screening

The screening period will be up to 28 days and begins by establishing the participant’s initial eligibility and signing of the informed consent form. Informed consent will be obtained prior to any study-specific procedures. Participants will be evaluated based on the inclusion and exclusion criteria (see [Section 6](#)) and will be enrolled using an Interactive Response Technology (IRT).

If a participant exceeds the 28-day screening period due to a study-related procedure (eg, scheduling of a tumor biopsy or waiting for a study-related laboratory value), the participant must be re-consented, but does not require a new participant identification number. In this situation, the fewest number of procedures from the initial screening should be repeated to qualify the participant, while maintaining participant safety and eligibility.

Re-enrollment after screen failure will be allowed. A new participant number will be assigned by the IRT at the time of re-enrollment. Imaging of the brain with magnetic resonance imaging (MRI) (with and without contrast) is required of all participants during Screening. Computed tomography (CT) of the brain (without and with contrast) can be performed if MRI is contraindicated. A 12-lead ECG is required during screening.

Tumor tissue must be obtained and submitted to a central laboratory prior to randomization. See [Section 6.1](#) and [Section 9.8.1](#) for specifications. The central laboratory must confirm receipt of evaluable tumor tissue as described in the Laboratory Manual prior to randomization. Assessment of tumor-cell PD-L1 expression by immunohistochemistry (IHC) must be performed by the central laboratory using pre-treatment tissue sample as described in the Laboratory Manual and results must be reported to IRT prior to randomization.

A pretreatment biopsy is required for enrollment into the study if an archived formalin-fixed paraffin-embedded (FFPE) sample less than 3 months old without any intervening therapy is unavailable for the participant.

5.1.2 Treatment Period

Treatment arms are illustrated in [Figure 5.1-1](#).

The randomized treatment period will assess efficacy and safety of BMS-986207 in combination with nivolumab plus ipilimumab (Arm A) versus nivolumab plus ipilimumab (Arm B).

After central laboratory confirmation of PD-L1 expression, approximately 180 participants (see [Section 10.2](#)) will be stratified by PD-L1 expression (< 1%, 1% - 49%, or ≥ 50%) and tumor histology (squamous versus nonsquamous) and randomized in a 2:1 ratio to:

- **Arm A:** Nivolumab 360 mg Q3W + ipilimumab 1 mg/kg Q6W + BMS-986207 600 mg Q3W
- **Arm B:** Nivolumab 360 mg Q3W + ipilimumab 1 mg/kg Q6W + placebo Q3W

Participants, investigators, and site staff will be blinded (single-blind) to treatment assignment. The DMC and Sponsor will be unblinded to treatment assignment for the purpose of safety evaluation. Treatment information access will not be used by the Sponsor to perform by-arm efficacy analyses. See [Section 5.1.4](#) for further information regarding the DMC and [Section 7.3](#) for further information regarding blinding. Additional information regarding blinding will also be provided in the statistical analysis plan (SAP).

All participants will be treated for up to 2 calendar years from start of study intervention regardless of treatment delays (up to 18 cycles, 42 days/cycle), until progression, unacceptable toxicity, death, or withdrawal of consent, whichever occurs first. Continuous safety evaluation and tumor assessment will guide the decision to treat a participant with additional cycles of study intervention if the participant has confirmed clinical benefit (up to a maximum of 2 years).

Dose reductions of study interventions are not permitted. Separate assessments of study interventions will be used in considering criteria for dose delay, resumption, and discontinuation (see [Sections 7.4.1](#), [7.4.2](#), and [8.1.1](#)).

Physical examinations, vital sign measurements, 12-lead ECG, and clinical laboratory evaluations will be performed at selected times throughout the dosing interval (see [Section 2](#)). Participants will be closely monitored for AEs throughout the study. Samples will be collected before and after study drug administration for PK analysis and pharmacodynamic parameter measurements (see [Section 9.5](#) for further details).

Imaging for tumor assessments will be performed according to [Section 9.4.5](#). Participants with unconfirmed progressive disease (PD), stable disease (SD), partial response (PR), or complete response (CR) at the end of a given cycle will continue to the next treatment cycle. Participants will be allowed to continue study intervention until the first occurrence of any of the following:

- Completion of up to 2 calendar years (up to 18 cycles) of study therapy, regardless of treatment delays
- PD defined by Response Evaluation Criteria in Solid Tumors (RECIST) v1.1 ([Appendix 5](#)) per investigator assessment, unless participants meet criteria for treatment beyond progression ([Section 8.1.2](#))

- Clinical deterioration suggesting that no further benefit from treatment is likely
- Intolerability to therapy
- Participant meets criteria for discontinuation of study intervention as shown in [Section 8.1](#)

Treatment beyond initial investigator-assessed RECIST v1.1 defined progression is permitted if the participant has investigator-assessed clinical benefit and is tolerating the treatment with discussion and agreement with Sponsor/Medical Monitor (or designee).

5.1.3 Follow-up Period

5.1.3.1 Safety Follow-up

At the end of treatment (EOT), all participants will enter a safety follow-up period upon completion of study intervention (up to a maximum of 2 years from first dose of study intervention, if applicable) or once the decision is made to discontinue the participant from treatment.

All participants will be evaluated for any new AEs (serious and non-serious) for at least 100 days after the last dose of study intervention. Follow-up visits should occur at Days 30, 60, and 100 (± 7 days for all study visits) after the last dose or date of discontinuation.

5.1.3.2 Imaging Follow-up

Participants that have discontinued treatment without having BICR-assessed disease progression will continue to have radiologic tumor assessments after treatment discontinuation for up to 2 years after last dose of study intervention as per [Table 2-3](#) (see [Section 9.1.1](#) for further details).

5.1.3.3 Survival Follow-up

Participants will be followed by phone contact or office visit every 12 weeks (± 2 weeks) until death, loss to follow-up, withdrawal of consent, or conclusion of the study, whichever comes first, for a period of up to 4 years from randomization. A follow-up more than 4 years after randomization could be considered in selected cases if an efficacy signal is apparent. Subsequent therapies will also be recorded in this survival follow-up period.

5.1.4 DMC and Other Committees

An independent DMC will be utilized to provide general oversight and safety considerations during the study. The independent DMC will provide advice to the Sponsor regarding actions the committee deems necessary for the continuing protection of participants enrolled in this study. The independent DMC will be charged with assessing such actions in light of an acceptable benefit-risk profile for nivolumab, ipilimumab, and BMS-986207. The independent DMC will act in an advisory capacity to BMS and will monitor participant safety data of the study.

BMS will have responsibility for the overall conduct of the study, including managing the communication of study data. BMS will be responsible for promptly reviewing the DMC recommendations, for providing guidance regarding the continuation or termination of the study, and for determining whether amendments to the protocol or changes to the study conduct are required. The DMC charter will describe the procedures related to the committee operations in

greater detail and will include an initial safety review after the first 12 randomized safety-evaluable participants have completed 6 weeks of treatment.

In addition to the DMC, BMS has in place a multi-layered process for ensuring participant safety through close collaboration of study site investigators, the BMS study team, and the BMS Worldwide Patient Safety (WWPS)-led SMT. This collaborative process constitutes the Data Safety Monitoring Plan for the study as detailed below.

- Study safety is evaluated continuously by representatives of BMS WWPS, who operate independently from the clinical team and monitor safety across all BMS protocols. AEs are monitored continuously by WWPS. Signal detection is performed at least monthly and ad hoc throughout the study by the SMT and composed, at a minimum, of the WWPS medical safety assessment physician (Chair of the SMT) and WWPS single-case review physician, the study Sponsor/Medical Monitor (or designee), the study biostatistician, pharmacovigilance scientist, and the epidemiologist. The SMT monitors actual or potential issues related to participant safety that could result in a significant change in the medical benefit-risk balance associated with the use of study intervention. Furthermore, investigators will be kept updated of important safety information during teleconferences between investigators and the BMS clinical team, which will be held on a regularly scheduled basis. If appropriate, select safety issues may be escalated to a senior-level, multidisciplinary, BMS-wide Medical Review Group for further evaluation and action. To support safety oversight, BMS has established an ongoing processes for collection, review, analysis, and submission of individual AE reports and their aggregate analyses.
- The SMT will review the totality of the safety data available throughout the study. Safety data will be continuously monitored and will be informed by a Bayesian framework (see [Section 10.5.1](#)). After considering overall safety and if an excessive number of pre-specified safety events are observed, an ad hoc data review by the DMC will be considered as needed.

The minutes of these meetings will be documented in the Trial Master File. The SMT will not share responsibilities with the DMC. Decisions on safety, toxicity, and benefit-risk will be solely the responsibility of BMS and will take account of the totality of the data available and in consideration of any DMC recommendations (see [Section 3.3](#) for additional details).

5.1.5 *Blinded Independent Radiology Central Review*

A BICR is recommended by regulatory agencies in situations where clinical site image interpretation is variable and results of image measurements are important for eligibility determination, safety, and/or efficacy endpoints. Specifically, BICR review of scans may mitigate bias regarding endpoint assessment due to the subjectivity involved in lesion measurement and interpretation of PFS. Sites should submit all images to BICR on a continuing basis. However, should the BICR interpretation be in conflict with the local evaluation, treatment decisions will be based on investigator assessment and not the BICR results provided to the site.

5.2 Number of Participants

Approximately 180 randomized participants are expected to be randomized in a 2:1 ratio to the 2 treatment arms stratified by PD-L1 expression and histology in pre-specified subgroups.

To ensure the randomized population is representative of the NSCLC population and to allow for appropriate subgroup analyses, total enrollment and/or enrollment in specific PD-L1 subgroups may be adjusted to ensure enrollment of at least 105 randomized participants with tumor cell PD-L1 expression $\geq 1\%$ with at least 75 randomized participants with tumor cell PD-L1 expression 1% - 49%, and at least 75 randomized participants with tumor cell PD-L1 expression $< 1\%$, based on central laboratory results.

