Table 5.4.2-1: Efficacy of Nivolumab + Ipilimumab vs Chemotherapy by Tumor PD-L1 Expression Level - CA209227 Part 1a and Part 1b

	PD-L1 < 1% (Part 1b)		PD-L1 ≥ 1% (Part 1a)		PD-L1 1% - 49% (Part 1a)		PD-L1 ≥ 50% (Part 1a)	
	Nivo + Ipi N = 187	Chemo N = 186	Nivo + Ipi N = 396	Chemo N = 397	Nivo + Ipi N = 191	Chemo N = 205	Nivo + Ipi N = 205	Chemo N = 192
OS								
HR (97.5% CI)	0.62 (0.47, 0.81)		0.79 (0.65, 0.96)		0.94 (0.73, 1.22)		0.70 (0.53, 0.93)	
Median	17.15	12.19	17.08	14.88	15.08	15.08	21.19	13.96
(95% CI), mo.	(12.85, 22.05)	(9.17, 14.32)	(14.95, 20.07)	(12.71, 16.72)	(12.16, 18.66)	(13.34, 17.54)	(15.51, 38.18)	(10.05, 18.60)
PFS per BICR (1° Definition)								
HR (97.5% CI)	0.75 (0.57, 0.99)		0.83 (0.69, 1.01)		1.15 (0.89, 1.50)		0.62 (0.47, 0.82)	
Median	5.06	4.70	5.06	5.55	4.01	5.49	6.74	5.59
(95% CI), mo.	(3.15, 6.37)	(4.21, 5.59)	(4.07, 6.31)	(4.63, 5.82)	(2.99, 5.52)	(4.37, 5.82)	(4.53, 11.01)	(4.57, 6.60)
ORR per BICR (CR + PR)								
Responders (%)	51 (27.3)	43 (23.1)	142 (35.9)	119 (30.0)	51 (26.7)	51 (24.9)	91 (44.4)	68 (35.4)
95% CI	(21.0, 34.3)	(17.3, 29.8)	(31.1, 40.8)	(25.5, 34.7)	(20.6, 33.6)	(19.1, 31.4)	(37.5, 51.5)	(28.7, 42.6)
DOR per BICR								
Median	17.97	4.83	23.16	6.24	12.22	7.59	31.84	5.75
(95% CI), mo.	(12.42, 28.65)	(3.71, 5.78)	(15.21, 32.16)	(5.59, 7.39)	(6.14, 16.07)	(6.24, 12.45)	(18.66, NA)	(4.47, 6.90)

Abbreviations: BICR, blinded independent central review; chemo, chemotherapy; CI, confidence interval; CR, complete response; CSR, clinical study report; DOR, duration of response; HR, hazard ratio; Ipi, ipilimumab; Nivo, nivolumab; Nivo + Ipi, nivolumab + ipilimumab; N, number; ORR, objective response rate; OS, overall survival; PD-L1, programmed death-ligand 1; PFS, progression-free survival; PR, partial response.

Source: Table 7.1.1.1-1 (Part 1a), Table 7.1.2-1 (Part 1b), (Figure S.5.120.5.309 (PFS-BICR), Figure S.5.326.4 9 (ORR-BICR), Table S.5.500.12 (PD-L1 1% - 49% DOR), Table S.5.128.1 (PD-L1 ≥ 50% DOR), and Table S.5.126.1.1 (PD-L1 ≥ 50% ORR-BICR), Table S.5.500.24 (PD-L1 ≥ 50% OS), Table S.5.500.25 (PD-L1 ≥ 50% PFS) of CA209227 Part 1 Final CSR.

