10.2 Sample Size Determination

The sample size of the study is calculated to have a sufficient probability of making the correct decision and have a low probability of making an incorrect decision under the pre-defined go criteria of primary efficacy endpoint of PFS in the PD-L1 $\geq 1\%$ subgroup. Using a Bayesian augmented control (BAC) design, a portion of the control cohort for Study CA020016 will be

borrowed from participants treated with nivolumab plus ipilimumab in Study CheckMate 227 whose baseline prognostic factors are similar to the current randomized population. Based on the results in the CheckMate 227 study, it is assumed that the median PFS in Arm B is 5 months with a constant HR of 0.605 of Arm A vs Arm B for the PD-L1 $\geq 1\%$ subgroup. The pre-defined go criteria at the end of the trial is probability (Pr) (HR < 1) > 0.9 and Pr (HR < 0.7) > 0.5. With the above assumption, 64 PFS events will need to be observed across the 2 arms, and there is 72.2% probability of making a go decision for a scenario at the interim analysis occurring at about 70% of the events, and 78.1% probability of making a go decision at the final analysis. This assumes 12 months for accrual and a minimum of 10 months follow up, for a total of 105 randomized participants with PD-L1 $\geq 1\%$ expression, with approximately 180 participants randomized under current assumptions of prevalence in the primary subgroup. The participants will be randomized to the BMS-986207 with nivolumab plus ipilimumab (Arm A) and the nivolumab plus ipilimumab (Arm B) in a 2:1 ratio.

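### At about 180 randomized, the PD-L1 minimums leave at most 30 of the 105 primary-population places for PD-L1 ≥ 50%, while the 5-month control median comes from a trial group that was 52% PD-L1 ≥ 50%

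*Combined protocol and SAP*

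**What the plan says.** Section 5.2 states: "Approximately 180 randomized participants are expected to be randomized in a 2:1 ratio". It then sets a floor of 105 for PD-L1 ≥ 1% and adds two further minimums: "at least 75 randomized participants with tumor cell PD-L1 expression 1% - 49%, and at least 75 randomized participants with tumor cell". The first of these applies within the 105; the second is for the stratum below 1%. No minimum is set for PD-L1 ≥ 50%. The purpose is given as: "To ensure the randomized population is representative of the NSCLC population and to allow for appropriate subgroup analyses". Section 5.2 lets the total, or recruitment within a PD-L1 stratum, be changed to reach these numbers. The synopsis and Section 10.2 repeat the minimums.

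Section 10.2 plans the primary comparison in PD-L1 ≥ 1% as follows: "Based on the results in the CheckMate 227 study, it is assumed that the median PFS in Arm B is 5 months". The HR is assumed constant at 0.605. The section says the total of 180 depends on a prevalence assumption but gives no figure for it.

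Table 5.4.2-1 ("Efficacy of Nivolumab + Ipilimumab vs Chemotherapy by Tumor PD-L1 Expression Level") gives the CheckMate 227 results by PD-L1 stratum. Sections 10.4.1.1 and 10.4.1.2 and Appendix 10 describe the borrowing. CheckMate 227 controls are chosen by propensity score, with PD-L1 expression listed as one example covariate, and their hazard centres the control prior.

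**The concern.** The minimums add up to the whole planned enrolment, so together they limit PD-L1 ≥ 50% without saying so. The planning median was observed in a group with nearly twice that limit's share of PD-L1 ≥ 50%, and in that trial this stratum had the longer PFS. The planning figures may therefore describe a different control group from the one the trial will recruit.

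The same gap matters for the borrowing. If the matched controls keep the CheckMate 227 PD-L1 mix, the prior makes Arm B look better than it is, and the estimated HR is pulled towards 1. Separately, the secondary estimates at PD-L1 ≥ 50% would rest on about 20 and 10 participants (30 split 2:1), which the plan does not disclose.

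**Working it through.** **1. The ceiling.** With both 75s met exactly:

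- N = 180: 180 − 75 − 75 = 30 at ≥ 50%; 30/105 = 28.6% of the primary population.
- N = 200: 200 − 75 − 75 = 50; 50/125 = 40.0%.
- CheckMate 227, nivolumab plus ipilimumab, PD-L1 ≥ 1% (Table 5.4.2-1): 205/396 = 51.8% at ≥ 50% and 191/396 = 48.2% at 1%-49%.
- Keeping the CheckMate split with 75 at 1%-49% needs 75/0.482 ≈ 155.5 at ≥ 1%, and 155.5 + 75 ≈ 230 in total.

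**2. The control median.** Inputs are the BICR median PFS values in Table 5.4.2-1: 4.01 months (1%-49%) and 6.74 months (≥ 50%). Assuming exponential PFS within each stratum, and writing w for the ≥ 50% share, the mixed median t solves

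(1 − w)·2^(−t/4.01) + w·2^(−t/6.74) = 0.5.

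- w = 205/396: t = 5.19 (0.197 + 0.303 = 0.500). The observed value is 5.06, so the approximation is within 3%.
- w = 30/105: t = 4.61 (0.322 + 0.178 = 0.500).
- w = 50/125: t = 4.88.

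The CheckMate 95% CI for the ≥ 1% median is 4.07 to 6.31, which contains 4.61.

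**3. Reproducing the stated go probability.** The Appendix 10 model was simulated with 70 versus 35 participants, 12-month accrual, 14 borrowed events and no dropout. The control prior is Gamma(14, 14·m/ln 2), where m is the prior median, and the log HR prior is effectively flat. Go requires Pr(HR < 1) > 0.9 and Pr(HR < 0.7) > 0.5. At HR 0.605 and 5 months:

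- Analysis at month 22 (12 + 10): 78.0%; the plan states 78.1%.
- Interim at 45 events: 72.6%; the plan states 72.2%.
- Analysis at exactly 64 events: 74.4%. The stated final figure matches the calendar cut, so both cuts are shown below.

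**4. The go probability at the quota mix, HR 0.605 in both strata.**

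| Scenario | Month-22 cut (6,000 trials) | 64 events (4,000 trials) |
|---|---|---|
| Control and prior at 5 months | 77.8% | 74.4% |
| Quota mix, prior of the same mix | 78.1% | 73.8% |
| Quota mix, prior left at 5 months | 74.5% | 70.6% |

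Monte Carlo error is about 0.5 to 0.7 points. At HR 1 with 64 events the go rates, in the same order, are 4.1%, 3.3% and 2.3%. A mismatched prior therefore costs correct go decisions and does not add false ones.

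**5. What the matching guarantees.** Section 10.4.1.1 does not say how PD-L1 is coded. If it is coded as ≥ 1% versus < 1%, the PD-L1 term cannot separate the two upper strata, and the matched ≥ 1% controls would be expected to keep roughly the 51.8% CheckMate share; a matching simulation gave about 51%. With three-level coding and 60 matches the simulated share ranged from 20% to 39%, around a target of 28.6%. These simulated shares are illustrative, since the documents give no covariate distributions. The balance check in Appendix 10 tabulates only binary covariates, which does not plainly cover a three-level factor.

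**The case against.** The strongest reply is that nothing in Section 5.2 is an arithmetic error. The minimums are floors that happen to sum to an approximate total, and that total may be adjusted. Nothing requires the CheckMate 227 mix to be reproduced. The 4.6 months is imprecise: it sits inside the CheckMate interval, and the stratum intervals overlap (2.99 to 5.52 and 4.53 to 11.01). The analysis prior is not fixed at 5 months but is estimated from matched controls, with PD-L1 among the listed covariates. Randomization is stratified on the same three categories, so the mix does not confound Arm A against Arm B. The objectives at PD-L1 ≥ 50% are for estimation only. Section 10.4.1.2 leaves detailed implementation to the SAP.

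Most of this stands, and it keeps the point modest. Three things remain. At N = 200 the ≥ 50% share is still at most 40%, and reaching the CheckMate share needs about 230 participants, a size that neither Table 10.2-1 nor the 12-month accrual assumption covers. Table 10.2-1 varies the HR, sample size and borrowing, but not the PD-L1 mix. A propensity score with PD-L1 as one example covariate does not fix the PD-L1 mix of the borrowed controls.

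A reader might also infer that the trial population is shown to be unrepresentative of NSCLC. The documents do not support that. They give no population PD-L1 prevalence, and one trial's split is not the population. What can be said is that the prevalence assumption behind 180 is not stated.

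**Conclusion.** The point holds as a gap in planning and in the borrowing rule. At about 180 randomized, PD-L1 ≥ 50% can supply at most 28.6% of the primary population, against 51.8% in the group behind the 5-month median. The matching Arm B median is about 4.6 months, compared with 5.2 by the same method at the CheckMate mix. Under a constant HR of 0.605, the go probability is essentially unchanged when the prior shares the trial's mix and about 4 points lower when it stays at 5 months.

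These figures assume exponential PFS within strata, equal HRs across strata, no dropout, 14 borrowed events, and both 75s met exactly.

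A reader might infer a much larger loss from the cited anti-TIGIT result at PD-L1 ≥ 50% (PFS HR 0.30), on the view that the benefit lies mainly in the stratum being limited. That would need assumed stratum-specific HRs. Section 10.2 assumes one constant HR for PD-L1 ≥ 1% and does not tie 0.605 to any PD-L1 mix, and the cited result concerns a different agent on an atezolizumab backbone. Nor do the documents show that 5 months is wrong, only that it belongs to a different mix.

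**What to change.** 1. In Section 10.4.1.1 and Appendix 10, match CheckMate 227 controls exactly on the three PD-L1 categories used for stratification, with propensity matching on the other covariates within each category. The borrowed hazard then has the trial's own PD-L1 mix. The donor pool is ample: 187, 191 and 205 for < 1%, 1%-49% and ≥ 50%. At the quota mix, 60 matches would need 25, 25 and 10, and 180 matches would need 75, 75 and 30. The cost is slightly fewer candidate donors per match.

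2. In Sections 5.2 and 10.2, state the assumed PD-L1 mix and the ceiling of 30 at N = 180. Rerun Table 10.2-1 with the Arm B median at that mix (about 4.6 months), as the base case or an added scenario. The cost is text and a simulation rerun, and the stated go probability may become slightly less favourable.

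Neither change adds participants.
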